11.1 Sponsor

The cost of the intervention, Luveris (rLH), will be covered by a research grant from the drug producing company EMD Serono. The grant will also cover the cost of additional supplies including syringes and needles. In addition, the study grant will cover the cost of AMH test, which estimated to cost 45 CAD per patient. The patient will not incur any additional costs by choosing to participate in this study.

12. Statistical analysis

12.1 Sample Size

A sample size calculation was performed according to the primary outcome of the total number of mature oocytes available for cryopreservation [28]. We assume the control group will have a mean of 8 cryopreserved oocytes with a standard deviation of 4 according to data from a previous meta-analysis of randomized trials evaluating FSH and LH versus FSH alone using a GnRH antagonist protocol [29]. We will use an alpha level of 5%, power of 80%, enrolment ratio of 1, and assume a 20% improvement in FSH and LSH versus FSH alone. This calculation will yield a sample size of 126 patients (n=63 per group). Accounting for 10% loss to follow-up, the total sample size will be 140 patients (n=70 per group). Reported p-values will be recorded as two-tailed. The following formula was used for sample size calculation, which was doubled to account for two trial arms and multiplied by 1.1 to account for 10% loss to follow-up:

$$n_1 = \frac{(\sigma_1^2 + \sigma_2^2/K)(Z_{1-\frac{\alpha}{2}} + Z_{1-\beta})^2}{|u_2 - u_1|^2}$$

$$n_1 = \frac{(4^2 + 4^2/1)(1.96 + 0.84)^2}{|10 - 8|^2}$$

$$n = 63 * 2 * 1.1$$

Where n_1 is the sample size for the FSH and LH group; σ_1^2 is the variance for FSH and LH group; σ_2^2 is the variance for the FSH only group; $Z_{1-\frac{\alpha}{2}}$ is the Z-score corresponding to an alpha level of 0.05; $Z_{1-\beta}$ is the Z-score corresponding to a power of 0.80; u_1 is the projected mean number of cryopreserved oocytes in the FSH and LH group; u_2 is the projected mean number of cryopreserved oocytes in the FSH only group; n is the total sample size after accounting for projected loss to follow-up

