7.6 Outcome measures

The primary outcome measure will be the total number of mature (MII) oocytes adjusted by antral follicle count (AFC) available for cryopreservation.

Secondary outcome measures will include the following:

- Total number of oocytes retrieved per cycle
- Ratio of mature (MII) to immature oocytes
- Total number of mature oocytes (MII) retrieved per IVF/ICSI cycle
- Oocyte yield (defined as the number of metaphase II (MII) oocytes retrieved divided by the number of follicles ≥15 mm on ultrasound on the day of trigger)
- "Follicular Output Rate" (FORT) (defined as ratio of pre-ovulatory follicles (16-22mm) on day of trigger × 100/AFC (3-8mm) [22]
- Incidence of moderate to critical OHSS based on the classification criteria by Golan et al [26].
- If the embryos are frozen:
 - o Fertilization rate, which will include two outcomes each defined as follows:
 - Definition 1: number of 2PN zygotes divided by the number of mature oocyte(s) fertilized per IVF/ICSI cycle.
 - Definition 2: number of 2PN zygotes divided by the number of oocytes incubated with at least 10,000 sperm per IVF cycle.
 - Total number of good quality day 5 embryos available for cryopreservation determined by an embryologist using the classification system by Gardner and Schoolcraft, 1999 [25].
- Dose-adjusted evaluation of the safety and tolerability of follitropin alfa + lutropin alfa compared to follitropin alfa as measured by incidence of:
 - o Treatment-emergent adverse events (TEAEs)
 - Treatment-related adverse events (AEs)
 - o Incidence of thromboembolic events

8. Study methods

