8.3 Study timeline

The duration of the trial, from the recruitment stage until completion, will vary depending on the amount of time needed to recruit patients for both arms of the study. Patients typically undergo a random start ovarian stimulation treatment, that ends with oocyte or embryo cryopreservation. Pregnancy rates are not part of the objectives of the study. Therefore, the timeline is expected to be between 2-3 months with each patient. The total duration of the study is expected to be 5 years (rounded up from 4 years 8 months) given 60% recruitment of 50 patients available at our site per year. Should fewer than expected number of patients be recruited at the 3-year mark, the study

period will be extended according to the observed annual recruitment calculated at 3 years for a maximum of 2 additional years.

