12.2 Planned analysis

The analysis will be performed on an intention-to-treat principle. Continuous variables will be examined for normality using a normal probability plot. Normally distributed continuous variables will be compared using Welch's t-test. Continuous variables not normally distributed will be compared using Mann-Whitney U test. Categorical data will be reported as counts with percentage, and compared with chi-square test or Fisher's exact test whenever appropriate. Additional sensitivity analysis will be performed taking into account potential confounding factors (i.e. Age, AMH, AFC). Regression analysis with age and FSH dose as factors will also be performed. Statistical analysis will be performed using R statistical software (R Foundation for Statistical Computing).

13. Trial registration

The clinical trial will be registered and available online at www.clinicaltrials.gov once the protocol is approved by the Mount Sinai Hospital Research Ethics Board.

14. Knowledge translation

The lack of consensus on the safety and efficacy of rLH in addition to FSH for ovarian stimulation calls for high quality randomized trials. Once the trial is completed and results are available, knowledge translation is of critical importance and involves the translation of findings to policy and practice [30]. Several procedures will be implemented to share the results of this trial internationally given the increasing number of young patients diagnosed with cancer. The study results will be firstly presented at international fertility conferences. The results will also be published in a high impact fertility journal, such as *Human Reproduction*. Experts in the field will be contacted to ensure they are aware of trial results.

15. Role of principal investigator

[name] is a reproductive endocrinologist at Mount Sinai Fertility as well as a Professor in the Department of Obstetrics and Gynecology at Mount Sinai Hospital. She will be supervising all aspects of the trial.

16. References

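### Section 12.1 states a 20% improvement but sizes the trial for 25% (10 versus 8 oocytes); power for 20% on the raw count is about 61% to 66%, not 80%

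*Protocol*

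**What the plan says.** Section 12.1 gives its assumptions in words and then as a formula.

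- Control arm: "We assume the control group will have a mean of 8 cryopreserved oocytes with a standard deviation of 4".
- Target: "power of 80%, enrolment ratio of 1, and assume a 20% improvement in FSH and LSH versus FSH alone".
- Formula with numbers inserted: "4^2 + 4^2/1)(1.96 + 0.84)^2}{|10 - 8|^2".
- Result: "This calculation will yield a sample size of 126 patients (n=63 per group").
- Loss: the per-arm figure is one "which was doubled to account for two trial arms and multiplied by 1.1 to account for 10% loss to follow-up", giving 140 in total, or 70 per group. P-values are two-tailed.

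Two other sections bear on the point. Section 7.6 defines the primary outcome: "The primary outcome measure will be the total number of mature (MII) oocytes adjusted by antral follicle count (AFC) available for cryopreservation". Section 8.3 gives the study duration: "expected to be 5 years (rounded up from 4 years 8 months) given 60% recruitment of 50 patients available at our site per year".

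**The concern.** The improvement is stated relative to FSH alone, and the FSH-alone mean is fixed at 8. A 20% improvement is therefore a mean of 9.6, a difference of 1.6 oocytes. The formula uses 2. The difference enters the formula squared, so going from 1.6 to 2.0 cuts the required sample size by 1 − (1.6/2.0)² = 36%.

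The stakes lie in how a null result would be read. Section 5 presents the trial as a definitive test of safety and efficacy. Section 6 says that if no significant difference is found, physicians will advise patients that adding LH brings no benefit. A reader of Section 12.1 would believe that a true 20% gain would be missed one time in five. If the real chance of missing it is well above that, a null result says much less about a 20% gain than the protocol implies.

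**Working it through.** **Inputs, all from Section 12.1:** control mean 8; SD 4 in both arms; two-sided 5%; power 80%; allocation 1:1; 10% loss.

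**Reproducing the plan's figure.** Per arm, n = (σ₁² + σ₂²)(1.96 + 0.84)² / Δ².

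- With Δ = 2: 32 × 7.84 / 4 = 62.72, so 63 per group and 126 in total. This matches.
- Loss: 63 × 1.1 = 69.3, rounded up to 70 per group, so 140 in total. This matches as well.

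**The size of the effect used.** (10 − 8)/8 = 25%. The stated 20% of 8 gives 8 × 1.20 = 9.6, so Δ = 1.6.

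**The same formula with the stated effect.** With Δ = 1.6: 32 × 7.84 / 2.56 = 98.0 per group. Unrounded z-values give 99, and the noncentral t distribution gives 100.

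**Power at the planned size.** By the normal approximation, power = Φ(Δ / (4√(2/n)) − 1.96). For Δ = 1.6 and n = 63, this is Φ(1.6/0.713 − 1.96) = Φ(0.285) = 61.2%. The full set:

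| Difference | n per group | Normal | Noncentral t |
|---|---|---|---|
| 1.6 (20%) | 63 | 61.2% | 60.6% |
| 1.6 (20%) | 70 | 65.8% | 65.2% |
| 2.0 (25%) | 63 | 80.1% | 79.5% |
| 2.0 (25%) | 70 | 84.1% | 83.6% |

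The rows with 63 are the protocol's own planning case after 10% loss. The rows with 70 assume that every randomised patient contributes an outcome. That is the upper limit, even under Section 12.2's rule: "The analysis will be performed on an intention-to-treat principle".

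**Smallest difference with 80% power (t):** 2.01 oocytes at 63 per group (25% of 8) and 1.91 at 70 per group (24%).

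**If the Mann-Whitney test is used,** which Section 12.2 allows, power for 1.6 is slightly lower. With relative efficiency 0.955 under normality, it is about 59% at 63 and 64% at 70.

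**What would rescue the stated figures.** For 1.6 oocytes, 63 per group and 80% power to hold together, the SD would have to be 1.6 × √(63/2) / 2.8 = 3.2. The protocol states 4.

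**The case against.** The strongest reply is that nothing is hidden. The formula is printed with its inputs, the total of 140 follows from it, and the trial calls itself exploratory. On this view the only slip is one percentage in the text; the test and its type I error are unaffected. Much of this stands, and it is why the repair is small. But the section makes a formal claim of 80% power for a named effect, and that claim is wrong as written. A reader can find the mismatch but cannot tell which number was intended.

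Two readings could explain the 10. The 20% may have been taken of 10 rather than 8, since (10 − 8)/10 = 20%. Or 9.6 may have been rounded up to a whole oocyte. The first conflicts with the text, which measures improvement against FSH alone. The second is not stated, and a mean count need not be a whole number. Neither makes the stated 20% consistent with 63 per group.

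A further objection is that these power figures do not describe the primary outcome, which is adjusted by AFC. That is correct. Power on the adjusted scale cannot be computed from the protocol and could be higher or lower. The 61% to 66% applies to the raw count, the same scale on which Section 12.1 makes its own claim.

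Finally, 66% is the no-loss figure. Under the protocol's planned 10% loss, 61% is the relevant one.

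**Conclusion.** The concern holds. A 20% improvement on a mean of 8, 80% power and 63 per group are incompatible. The sample size is right for 25%, not 20%. On the protocol's inputs (raw count, SD 4 in both arms, two-sided 5%, comparison of means), power for the stated 20% is about 61% with 63 evaluable per group and at most 66% with all 70. The claim is thus 14 to 19 percentage points too high. A true 20% gain would be missed about 34% to 39% of the time instead of 20%. Nothing elsewhere in the protocol reconciles text and formula.

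**What to change.** The sponsor should first state which effect was intended, then make the text and formula of Section 12.1 agree.

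With the total kept at 140, replace the 20% in the text with *a 25% improvement (8 to 10 oocytes)* and add: *Power for a 20% improvement (1.6 oocytes) is about 61% at 63 evaluable per group and up to 66% with no loss. These figures are for the raw mature oocyte count, not the AFC-adjusted primary outcome of Section 7.6.* If 20% was the intended target, the formula should read |9.6 − 8|, and the claim of 80% power has to be withdrawn at this sample size.

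The cost is a wording change and two sentences, with no extra patients and no change to the analysis. The price is an openly larger target effect and a lower stated power for 20%.

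Keeping both 20% and 80% power is hardly feasible within the protocol's own timeline. It needs 98 to 100 per group, or 216 to 220 enrolled after the protocol's factor of 1.1 (for example, 98 × 2 × 1.1 = 215.6). That is 76 to 80 more patients. At 0.60 × 50 = 30 a year it takes 7.2 to 7.3 years. The planned 5 years plus the maximum 2-year extension in Section 8.3 would yield 7 × 30 = 210.

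In the same edit, correct the order of the means. By the legend, u₂ is the FSH-only mean, yet the printed numbers put 10 in that position. The absolute value makes this harmless to the result.

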12.2 Planned analysis

The analysis will be performed on an intention-to-treat principle. Continuous variables will be examined for normality using a normal probability plot. Normally distributed continuous variables will be compared using Welch's t-test. Continuous variables not normally distributed will be compared using Mann-Whitney U test. Categorical data will be reported as counts with percentage, and compared with chi-square test or Fisher's exact test whenever appropriate. Additional sensitivity analysis will be performed taking into account potential confounding factors (i.e. Age, AMH, AFC). Regression analysis with age and FSH dose as factors will also be performed. Statistical analysis will be performed using R statistical software (R Foundation for Statistical Computing).

13. Trial registration

The clinical trial will be registered and available online at www.clinicaltrials.gov once the protocol is approved by the Mount Sinai Hospital Research Ethics Board.

14. Knowledge translation

The lack of consensus on the safety and efficacy of rLH in addition to FSH for ovarian stimulation calls for high quality randomized trials. Once the trial is completed and results are available, knowledge translation is of critical importance and involves the translation of findings to policy and practice [30]. Several procedures will be implemented to share the results of this trial internationally given the increasing number of young patients diagnosed with cancer. The study results will be firstly presented at international fertility conferences. The results will also be published in a high impact fertility journal, such as *Human Reproduction*. Experts in the field will be contacted to ensure they are aware of trial results.

15. Role of principal investigator

[name] is a reproductive endocrinologist at Mount Sinai Fertility as well as a Professor in the Department of Obstetrics and Gynecology at Mount Sinai Hospital. She will be supervising all aspects of the trial.

16. References

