Fertility preservation is performed before the initiation of cancer therapy in an effort to reduce its cytotoxic effects on ovarian function. However, recent literature has demonstrated that ovarian function is reduced in cancer patients even before starting cancer treatment. A case series reported a greater proportion of immature oocytes per cycle and lower maximal levels of estradiol in various cancer patients compared to patients with isolated tubal infertility, suggesting the negative impact

of cancer on oocyte maturation [12]. A matched cohort study reported lower AMH levels in patients with lymphoma before chemotherapy, warranting higher doses of gonadotropins for ovarian stimulation to maximize the number of oocytes retrieved before chemotherapy [13].

Studies have highlighted that administration of exogenous FSH and LH is essential for patients with hypogonadotropic hypogonadism [23], which is consistent with the current approved use of rLH by Health Canada. Evidence also supports the use of rLH in poor responders with advanced maternal age [9]. There is growing concern in the literature that some oncology patients may be poor responders prior to cancer therapy due to hypothalamic gonadal axis dysfunction secondary to their malignancy [2]. With evidence suggesting that the hypothalamic gonadal axis is affected in the oncology population, and that rLH may improve fertility preservation outcomes in a subgroup of patients that mimic hypogonadotropic cases, the efficacy of rLH in oncology patients is plausible.

Given the mixed literature of rLH efficacy in the oncology population and the improved fertility preservation outcomes in various patients supplementing ovarian stimulation with rLH, an exploratory randomized controlled trial is warranted to definitively address the safety and efficacy of rLH in non-hormone sensitive cancer patients.

6. Significance of the study

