7.1 Study design

The proposed study is an open-label, exploratory, randomized control trial examining the effect of FSH and rLH (Luveris) versus FSH alone on the number of mature oocytes available for cryopreservation in non-hormone sensitive onco-fertility patients. These patients include those diagnosed with malignancy other than breast, uterine and ovarian cancer.

Given that the care of oncology patients is time sensitive, a random start of the treatment cycle is the usual approach in our clinic, with no prior priming. The patient has a random serum levels of estrogen, progesterone, LH, FSH and HCG levels obtained. A transvaginal ultrasound is performed

as well, and the stage of the cycle is determined. Based on the stage of the cycle, gonadotropin starting time is planned accordingly and the starting dose will be individualized based on AFC as detailed below.

- Early follicular phase: Gonadotropin stimulation started. A GnRH antagonist will be given once the dominant follicle measures >1.4 cm.
- Mid to late follicular phase: patients who have a dominant follicle >1.5 cm with an E2 >300 and a progesterone <5 will be triggered usually with HCG (Ovidrel 250 mcg subcutaneous). After three days gonadotropin stimulation is started.
- Start of luteal phase: start gonadotropin stimulation and once the dominant follicle measure >1.4, a GnRH antagonist will be given.

Patients will be randomly assigned in a 1:1 ratio to either treatment or control group. Treatments in each of the trial arms will be as follows:

- a) Treatment arm: Patients will self-administer a subcutaneous injection of Gonal-F (FSH) in addition to Luveris daily until a pre-set criteria to trigger ovulation is reached.
- b) Control arm: Patients will self-administer a subcutaneous injection of Gonal-F (FSH) alone daily until a pre-set criteria to trigger ovulation is reached.

Transvaginal ultrasound and bloodwork monitoring is initiated to monitor the ovarian response. Once the patient meets one of the following two criteria

- a) A serum estradiol (E2) of greater than 2,000 pmol/L
- b) A follicle measuring greater than 14 mm,

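### The primary comparison is left to a normality plot and ignores AFC and the age stratum, while the protocol describes the primary outcome in three different ways

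*Protocol*

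**What the plan says.** **Choice of test (section 12.2).** "Continuous variables will be examined for normality using a normal probability plot". Variables judged normal go to Welch's t-test; for the rest, "Continuous variables not normally distributed will be compared using Mann-Whitney U test". No criterion for reading the plot is given, and no separate analysis is named for the primary outcome.

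**Covariates (sections 8.1, 8.2, 12.2).** Randomisation is stratified by age, at most 35 against over 35. Section 8.2 reports that, in the centre's own data, AFC and AMH were the only independent predictors of the number of mature oocytes. In section 12.2, AFC is a covariate only in an additional sensitivity analysis, alongside age and AMH. A further sentence reads "Regression analysis with age and FSH dose as factors will also be performed", without AFC.

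**Primary outcome.** The descriptions differ:

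- Section 3: a proportion of mature oocytes relative to AFC.
- Section 7.6: "total number of mature (MII) oocytes adjusted by antral follicle count (AFC) available for cryopreservation".
- Section 7.1: the effect of FSH plus rLH "versus FSH alone on the number of mature oocytes available for cryopreservation in non-hormone sensitive onco-fertility patients", with no mention of AFC.
- Section 12.1: sized on the plain total, called the primary outcome.
- Section 7.6 also lists the MII total per cycle as a secondary outcome.

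**Status of the trial.** Section 7.1: "The proposed study is an open-label, exploratory, randomized control trial". Section 5: an "exploratory randomized controlled trial is warranted to definitively address the safety and efficacy of rLH".

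**The concern.** Welch compares means and Mann-Whitney compares rank order, so the plot decides the effect reported as well as the p-value. That decision is a visual judgement made once outcomes are in hand, in an open-label trial.

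The test also fits the outcome poorly. If adjustment by AFC means covariate adjustment, neither test does it. If it means dividing by AFC, section 7.6 should say so, and section 12.1 has sized a different quantity. Because the plain MII total is separately listed as secondary, the ratio is the likeliest reading under a two-group test, but sections 7.1, 7.6 and 12.1 do not state it.

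Two things are at stake. A count and a ratio can lead to different conclusions from the same data. And dividing by AFC removes its influence fully only if MII rises in proportion to AFC; otherwise the ratio test gives up precision that baseline data already collected could recover.

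**Working it through.** **1. The protocol's own figure.** Section 12.1 uses SD 4 in each arm, two-sided alpha 5%, power 80% and a difference of 10 − 8 = 2:

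n per group = (4² + 4²)(1.96 + 0.84)² / 2² = 32 × 7.84 / 4 = 62.72, rounded up to 63.

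Then 126 / 0.9 = 140. The figure reproduces, as a comparison of mean plain counts with an unadjusted SD. It does not size a ratio, an AFC-adjusted analysis or a rank test. (The stated 20% gain on 8 is 1.6, not 2. That is a separate matter; the simulations below use the stated 20%.)

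**2. Inputs for the simulation.**

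- From the protocol: 63 per arm, control mean 8, SD 4, 20% gain, age-stratified allocation.
- Assumed, because the protocol gives no AFC distribution: AFC gamma with mean 15 and SD 4, 5 or 6, rounded, minimum 1; mean MII = c × AFC^b with b = 0.5, 0.75 or 1; Poisson-gamma counts; 25% aged over 35 with no age effect.
- 2,000 trials per setting. The model is Poisson with HC1 robust standard errors.

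The combination b = 1 with AFC SD 6 cannot be run. The variance of the mean would be (8 × 6/15)² = 10.24, and adding the Poisson variance of 8 gives 18.24, above the total of 4² = 16.

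**3. Power at a 20% gain.**

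| b | AFC SD | Ratio, Welch | Ratio, Mann-Whitney | Log-AFC Poisson model |
|---|---|---|---|---|
| 0.5 | 4 | 0.520 | 0.519 | 0.580 |
| 0.5 | 5 | 0.520 | 0.531 | 0.614 |
| 0.5 | 6 | 0.499 | 0.513 | 0.609 |
| 0.75 | 4 | 0.591 | 0.571 | 0.613 |
| 0.75 | 5 | 0.633 | 0.615 | 0.677 |
| 0.75 | 6 | 0.657 | 0.665 | 0.748 |
| 1 | 4 | 0.690 | 0.679 | 0.710 |
| 1 | 5 | 0.779 | 0.769 | 0.807 |

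A repeat of b = 0.5, SD 6 with 4,000 fresh trials gave 0.498 / 0.514 / 0.625. Over the two ratio tests, the model gains 6–13 points at b = 0.5, 2–9 at b = 0.75 and 2–4 at b = 1.

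**4. Effect of the choice of test.**

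- Welch and Mann-Whitney on the ratio disagree on significance in 6–11% of trials at a 20% gain and in 2.0–3.5% under the null. This is an upper limit on what the plot can change.
- Two readers of the plot, represented by Shapiro-Wilk at p < 0.05 and p < 0.001, pick different tests in 14–45% of trials and differ on significance in 1–3%.
- On plain counts (negative binomial, mean 8, SD 4), Shapiro-Wilk at 5% flags non-normality in about 89–91% of trials. Mann-Whitney would then usually replace the comparison of means used for sizing.

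**5. Effect of the outcome definition.** Welch on the plain count and Welch on the ratio reach different significance verdicts in 17–33% of trials with a true effect, and in about 6–7% under the null.

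**6. Type I error.** In seven settings the plot rule rejects in 4.3–5.4% and the model in 4.4–5.4%. The eighth (b = 0.5, SD 6) gave 6.4–6.8% in 2,000 trials and 5.0–5.2% in 8,000 fresh ones. On plain counts, taking whichever of Welch and Mann-Whitney is more favourable gives about 6.1%.

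**7. Cross-check on the plain count.** With residual SD = 4 × √(1 − ρ²), where ρ is an assumed correlation of AFC with the count, power at 63 per arm for a difference of 1.6 rises from 0.61 unadjusted to 0.65, 0.74, 0.80 and 0.88 at ρ = 0.3, 0.5, 0.6 and 0.7.

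**The case against.** The plot rule does little measurable harm: type I error stays near 5%, and two readers would differ on significance in only 1–3% of trials. **This stands.** The case against the rule is that it leaves the effect measure unfixed, not that it inflates error.

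On the ratio reading AFC is already inside the outcome, and section 12.2 plans covariate analyses, so adjustment is secondary rather than absent. **This stands in part.** The age stratum is still missing from the primary comparison, and the ratio reading has to be inferred.

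The power gain depends on AFC inputs that the protocol does not give, and it is only 2–4 points if MII is proportional to AFC, arguably the premise of an AFC-relative outcome. **This stands**, and is why a range is shown.

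The Poisson model is one sound choice among several; it omits AMH, and age was given no effect in the simulation. **True.** Section 8.2 says AMH is not available when treatment starts and names only AFC and AMH as independent predictors, so the age term may add little precision. It is there because randomisation was stratified on age.

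Model detail is normally left to an SAP, and the trial calls itself exploratory. An SAP can supply detail, but whichever outcome it adopts will still contradict another section of the protocol. Section 5 also expects a definitive answer, and section 6 foresees physicians counselling against rLH after a null result.

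**Conclusion.** The concern holds. The protocol does not fix what the primary outcome is, and the only comparison it offers is chosen from the outcome data and uses neither AFC (unless a ratio is meant) nor the age stratum. The definition is the weightier half: count and ratio readings part company in 17–33% of simulated trials, against at most 6–11% for the choice of test on the ratio. The power forgone by a ratio test is 2–13 points, depending on how steeply MII rises with AFC.

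The direction rests on the protocol's text. The sizes rest on assumed AFC values (mean 15, SD 4–6) and assumed exponents (0.5 to 1). Type I error is not the issue. This should be corrected before analysis, but it does not invalidate the design.

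**What to change.** - **Name one primary analysis:** a Poisson model of the MII count on arm, log AFC and age stratum (at most 35, over 35), with robust standard errors, reporting the rate ratio and its 95% CI. State that this is what adjustment by AFC means. A log-AFC slope of 1 corresponds to the ratio reading and a slope of 0 to the plain count, so neither need be assumed.
- **Align** sections 3, 7.1, 7.6, 12.1 and 12.2 with that definition, and keep the unadjusted MII total as a distinct secondary outcome.
- **Delete the plot-based choice** for the primary outcome. Always report the MII/AFC ratio by both Welch and Mann-Whitney as sensitivity analyses.
- **AFC of 0:** both the ratio and log AFC are then undefined. If such patients can enter, specify log(AFC + 1) from the start; power was within 0.2 points of log AFC.
- **Minor:** state that FSH dose in the supplementary regression is the AFC-based starting-dose group of section 8.2, not the total dose accrued after randomisation.

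**Cost:** a protocol amendment and no new data. If a ratio was intended, the estimand changes from MII/AFC to an AFC-adjusted count. If the sponsor prefers the ratio, the minimum is to say so in every section, name one test and size the trial on it.
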